2.3.2. Benefit Assessment

For healthy participants participating in this study, no clinical benefit is expected.

2.3.3. Overall Benefit/Risk Conclusion

Sisunatovir is not expected to provide any clinical benefit to healthy participants in this study.

Taking into account the measures to minimize risk to study participants, the potential risks identified in association with sisunatovir are justified by the anticipated benefits that may be afforded to participants with RSV.

3. OBJECTIVES AND ENDPOINTS

Objectives	Endpoints
Primary:	Primary:

To evaluate the effect on QT interval corrected for heart rate (QTc) interval in healthy participants, of possible clinical therapeutic concentrations of sisunatovir compared with placebo.	
Placebo-corrected, baseline adjusted QTc interval using Fridericia's correction method (QTcF) of sisunatovir at expected maximum concentrations (C_{max}) at the CCI [REDACTED].
Secondary:	Secondary:

To evaluate the safety and tolerability at possible clinical therapeutic concentrations of sisunatovir, including but not limited to cardiovascular safety.To determine study sensitivity by comparing the effect of moxifloxacin 400 mg on QTc interval with placebo at historical moxifloxacin time for maximum observed concentration (T_{max}) of 3-5 hours.	
Adverse event (AE), ECG assessments, vital sign measurements, and clinical safety laboratory measurements.Baseline adjusted QTcF of moxifloxacin and placebo at T_{max} of 3, 4, and 5 hours on Day 3.
Exploratory:	Exploratory:

To evaluate the effect of sisunatovir on the electrocardiogram (ECG) parameters of, heart rate, PR interval and QRS interval.To evaluate the plasma pharmacokinetics (PK) of sisunatovir following multiple oral doses.To explore PK of sisunatovir by microsampling technique.	
Baseline adjusted heart rate, PR interval, and QRS intervals of sisunatovir and placebo at each postdose time point.Plasma sisunatovir parameters, including C_{max}, T_{max} and area under the plasma concentration-time profile from time 0 to 24 hours (AUC₂₄) post-dose on Day 3.Concentration of sisunatovir from paired samples obtained via microsampling compared to venous sampling.

4. STUDY DESIGN

4.1. Overall Design

This is a Phase 1, multiple-dose, randomized, 3-treatment, 3-period cross-over, 6-sequence, sponsor-open, placebo-and positive-controlled study to be conducted in approximately 42 adult healthy participants under fed conditions. Approximately 42 participants will be randomized into 6 sequences with 7 participants in each sequence. Participants assigned to treatment A will receive [REDACTED] oral doses of sisunatovir administered CCI [REDACTED] over [REDACTED] days in a

fed state. Participants assigned to treatment B will receive [redacted] oral doses of matching placebo administered [redacted] CCI [redacted] over [redacted] days in a fed state. Participants assigned to treatment C will receive [redacted] oral doses of placebo administered [redacted] CCI [redacted] for [redacted] days followed by a single dose of 400 mg moxifloxacin on the morning of Day [redacted]. Treatment assignments to sisunatovir and placebo will be blinded to the participants, investigator and CRU staff (except pharmacy staff) but open to the sponsor. Moxifloxacin administration on Day [redacted] will be unblinded.

For individual participants, the total duration of participation from the screening visit to the follow-up visit will be approximately 14 weeks. Screening evaluation will occur within the 28 days prior to dosing in the first treatment period. During each treatment period, eligible participants who meet the entry criteria will be admitted on Day -1, prior to treatment administration on Day 1, and will reside in the PCRU until completion of protocol assessments on Day 4. Participants may be discharged between study periods at the discretion of the investigator. There will be a washout of at least 7 days between dose administrations in consecutive crossover treatment periods. Follow-up contact will be made at least 28 calendar days and up to 35 calendar days after the last administration of the investigational product to capture any potential AEs and concomitant treatments, and to confirm appropriate contraception usage. Contact with the participant may be done via phone. For each participant, the duration of participation from Period 1 admission to discharge will be approximately 4 weeks. The follow-up call will occur up to 5 weeks after last dose of study drug.

4.2. Scientific Rationale for Study Design

This purpose of this study is to assess the effect of sisunatovir on QT interval as recommended by the ICH E14 guideline and in ICH E14 Q&As (R3).⁵ The concentration-QT analysis is defined as the primary analysis in this study and serves as the primary basis for the decision to classify the QT prolongation risk for sisunatovir.

Preliminary CCI [redacted] analysis of SAD and MAD data (C5241001) for sisunatovir suggested that overall, the model predicts CCI [redacted] doses of up to CCI [redacted] mg and CCI [redacted] doses of up to CCI [redacted] mg of RV521 with CCI [redacted] on ECG parameters. The effects of sisunatovir on QT interval was evaluated in Part A (single dose administration) of the study. This part of the study did not include a placebo group, but since the lowest dose (10 mg) resulted in exposure below the limit of detection, the data from this group was used as a surrogate for placebo. A model was built to investigate the effect of RV521 on QTcF at concentrations seen in Part A of the study. In particular, predictions of the effect at the geometric mean of the individual C_{max} values under each dose with quantifiable concentration and at least 6 participants were given together with two-sided 90% confidence intervals. As the results CCI [redacted] any effect of RV521 on CCI [redacted], and, indeed indicate no effect at all, a more in-depth investigation into the appropriateness of the assumption of linearity or absence of PK-PD-hysteresis was not considered necessary. A similar evaluation was performed for data obtained from Part B (placebo controlled, multiple dose administration) and a similar conclusion was reached where no effect of treatment on QTcF was observed.

In order to achieve therapeutic concentrations the current study will dose to steady state, which is achieved after approximately CCI [redacted] so the current study will evaluate

QTc interval at steady state on Day 3. As the exposure of sisunatovir increases in a greater than dose proportional manner, the current study will evaluate the highest feasible dose that is projected to be well tolerated. In this study, an initial dose of [REDACTED] mg has been selected to achieve high clinical exposure based on interpolation between the [REDACTED] mg and [REDACTED] mg exposures observed in [REDACTED]. The safety and PK data from approximately the first 7 participants may be assessed and if observed exposure of [REDACTED] is lower than predicted (see [Table 3](#)) and does not cover the high clinical exposure, then the dose will be increased to [REDACTED].

The effect of food on the pharmacokinetics of sisunatovir has been variable in Phase 1 studies. However, the effect of food on the pharmacokinetics of sisunatovir using the formulation to be used in this study (dry powder blend in capsules) showed minimal food effect. The current study will administer study intervention under fed conditions. The impact of food on ECG measurements will be controlled by consistent timing and content of meals across sisunatovir, placebo, and moxifloxacin treatments.

A concurrent placebo control will be included in accordance with ICH E14 recommendations to enhance the validity of this study and to avoid potential biases associated with study procedures.

To increase the confidence that this study has the ability to detect a QTc prolongation in the range of approximately 5 ms, a concurrent positive control will be included to establish assay sensitivity. In this study, moxifloxacin will be used as the active control. Moxifloxacin is a fluoroquinolone antibiotic that produces consistent and predictable QT prolongation and is routinely used as a positive control in TQT studies. Based on recent Pfizer experience from TQT trials conducted at internal CRUs using automated readings, a single 400 mg dose of moxifloxacin produces a maximum mean heart rate-corrected QT interval using Fridericia's correction (QTcF) change from baseline between 7.9 msec and 11.0 msec 2 to 5 hours postdose time points with machine readings. The t_{max} of moxifloxacin is delayed by ≥ 1 hour when administered under fed conditions^{8,9}, with delays in the peak effects on QTc to 4 hours post-dose⁹. Encapsulation of commercially available moxifloxacin tablets to achieve blinding has the potential to have an impact on absorption, therefore encapsulation will not be employed and moxifloxacin will be administered on Day 3 in an open manner. Blood samples from participants randomized to placebo or moxifloxacin will be collected and retained, but will not be routinely analyzed.

All ECG measurements will be performed in triplicate at each nominal sampling time (see [Schedule of Activities](#) and [Electrocardiogram Section 8.3.3](#)). Triplicate measurements are intended to reduce the intrinsic variability and measurement error associated with ECG measurement of the QT/QTc interval. The collection of ECGs at multiple time points is performed to take into consideration the diurnal pattern and variability of QT intervals, dependent upon multiple factors including activity level, postural changes, circadian patterns and food ingestion. The sampling time points have been chosen based on the expected PK profiles of sisunatovir and moxifloxacin. The time to reach maximum concentration (T_{max}) for sisunatovir is approximately 4 to 6 hour postdose based on previous Phase 1 and 2 studies

(Summary of sisunatovir Pharmacokinetics Section 8.5). This schedule will also allow peak QT effects with moxifloxacin, to be captured.⁷

To minimize the risks of COVID-19 related complications to participants and the study site personnel, assessment of risk for, symptoms of or testing for COVID- 19 may be performed at screening, admission to the CRU, and/or at other times during the study at investigator discretion and according to local site policies.

As this is healthy participant study, the use of concomitant medications in this study is expected to be minimal. Nevertheless, according to the DDI risk assessment for sisunatovir as described in Section 2.2.2, sisunatovir is a moderate inhibitor of CYP3A4 and is projected to be a weak inhibitor of CCI [REDACTED]. For this reason sensitive and narrow TI CYP3A4 substrates and sensitive and narrow TI CCI [REDACTED] substrates are prohibited in this study. Since sisunatovir is a P-gp and CYP3A4 substrate, strong and moderate CYP3A4 and P-gp inhibitors or inducers are prohibited. Lastly, due to risk of CCI [REDACTED] and CCI [REDACTED] inhibition, sensitive substrates of these transporters are prohibited. Use of specific prohibited prior/concomitant therapies are outlined in [Appendix 9](#).

4.2.1. Choice of Contraception/Barrier Requirements

There is no suspicion of human teratogenicity based on the intended pharmacology of the compound. Human reproductive safety data are limited for sisunatovir, therefore the use of a highly effective method of contraception is required for all fertile participants (see [Appendix 4](#)).

4.3. Justification for Dose

Considering the exposure of sisunatovir increases in a greater than dose proportional manner, the current study will evaluate the highest feasible dose that is well tolerated. The pharmacokinetics of CCI [REDACTED] mg and CCI [REDACTED] mg Q12 hour doses have been evaluated in study CCI [REDACTED] with the same formulation that is to be used in this study (draft PK data available, final reporting pending). Draft results from CCI [REDACTED] indicate that the CCI [REDACTED] mg Q12hr sisunatovir dose under fed conditions resulted in mean exposure above rat NOAEL associated with the 28-day GLP study, whereas exposures associated with 200 mg Q12hr were consistent with those observed in previous Phase 1 studies with sisunatovir, including the human challenge study (C5241002). As of 4 April 2023, in study CCI [REDACTED] there have been no SAEs attributable to sisunatovir and no study drug discontinuation due to an AE. The most common AEs are GI related (nausea, diarrhea, abdominal pain/distention), consistent with previous studies. No clinically meaningful trends were seen with ECG parameters, vital signs or laboratory values.

In this study, an initial dose of CCI [REDACTED] has been selected. [Table 3](#) shows the anticipated mean steady-state exposure at the Phase 2/3 clinical dose (200 mg Q12hr) as well as the predicted mean exposure at CCI [REDACTED] in this study based on interpolation between the CCI [REDACTED] mg and CCI [REDACTED] mg exposures observed in CCI [REDACTED]. [Table 3](#) also compares projected exposure at the CCI [REDACTED] mg dose level to that observed at the NOAEL in the 28-day rat

GLP toxicology study. These data indicate that the expected exposure at the **CCI**-mg dose level is comparable to the rat NOAEL.

Table 3. Summary of Preliminary (Unaudited) Plasma PK Parameters of Sisunatovir Following Multiple Oral Dose Administration for 5 Days in Healthy Participants in **CCI, Compared to Predicted Exposures relative to Rat NOAEL**

Parameter ^a , Units	CCI mg Q12hr (fed), n=12 ^b	CCI mg Q12hr (fed), n=5	Predicted 250 mg Q12hr (fed)	Predicted 300 mg Q12hr (fed)	Predicted DDI effect on 200 mg Q12hr (fed)	Rat NOAEL 60 mg/kg/day
Day 5 (Steady State)						
C _{max} (ng/mL)	97.9 (65)	811.0 (41)	CCI	CCI	CCI	322
AUC _{tau} (ng·hr/mL)	787.3 (76)	7245.2 (47)	CCI	CCI	CCI	4725 ^c

a geometric mean (geometric %CV).

b Data collected from 9 participants. 3 participants received **CCI** mg (fed) in Period 1 and repeated in Period 2 after washout period.

c AUC over 24 hours.

Following evaluation of safety and sisunatovir PK data from at least 7 participants in this study, at Sponsor discretion the dose of sisunatovir may be increased to **CCI** provided that the projected exposure at the higher dose is no more than 20% above the rat NOAEL mean exposures for the 28 day GLP tox study. These predicted exposures would be well below the observed exposure with an acceptable safety profile from the ongoing study **CCI**. This will allow characterization of concentration-QTc analysis at higher exposures to more fully understand the potential effects at high clinical exposures.

Given the exposures of **CCI** mg Q12hr exceeded NOAEL exposures with an acceptable safety profile (Study **CCI**), robust monitoring of participants in the PCRU, limited duration of dosing, and variability in exposure at NOAEL of 60 mg/kg/day, crossing the mean NOAEL limits would not pose a safety concern for participants. Additionally, the toxicity findings above the NOAEL (120 mg/kg/day) were predominantly transient in nature and reversed after 14 days off treatment.

In study C5241004, coadministration with itraconazole, a strong CYP3A inhibitor, increased exposure of sisunatovir by approximately 3 to 3.5-fold. Thus, the predicted high clinical exposure for 200 mg Q12 hours under fed conditions is a C_{max} of **CCI** ng/mL and AUC_{tau} of **CCI** ng·hr/mL. The safety and PK data from approximately the first 7 participants may be assessed and if observed exposure of **CCI** under fed conditions is lower than predicted (see Table 3) and do not cover the high clinical exposure, then the dose will be increased to **CCI**, as described above. A single 400 mg dose of moxifloxacin has been used as standard positive control in QT studies and will be included as an open-label treatment.

In order to achieve therapeutic concentrations the current study will dose to steady state. Phase 1 studies indicate that steady state is achieved after approximately [REDACTED] CCI [REDACTED] so the current study will evaluate QTc interval at steady state on Day [REDACTED]. Treatment A and B will receive sisunatovir and placebo [REDACTED] CCI [REDACTED] for [REDACTED] doses, respectively. To maintain consistency between treatment groups, Treatment C will consist of placebo [REDACTED] CCI [REDACTED] for [REDACTED] days ([REDACTED] doses) and moxifloxacin administered on Day [REDACTED].

4.4. End of Study Definition

The end of the study is defined as the date of the last visit of the last participant in the study.

A participant is considered to have completed the study if they have completed all periods of the study, including the last visit.

5. STUDY POPULATION

This study can fulfill its objectives only if appropriate participants are enrolled, including participants across diverse and representative racial and ethnic backgrounds. Use of a prescreening tool is utilized for study recruitment purposes, it will include collection of information that reflects the enrollment of a diverse participant population including, where permitted under local regulations, age, sex, and race, and ethnicity. The following eligibility criteria are designed to select participants for whom participation in the study is considered appropriate. All relevant medical and nonmedical conditions should be taken into consideration when deciding whether a particular participant is suitable for this protocol.

Prospective approval of protocol deviations to recruitment and enrollment criteria, also known as protocol waivers or exemptions, is not permitted.

5.1. Inclusion Criteria

Participants are eligible to be included in the study only if all of the following criteria apply:

Age and Sex:

1. Participants aged 18 to 65 years, inclusive, at the time of signing of the ICD.
 - All fertile participants must agree to use a highly effective method of contraception (See [Appendix 4](#)).
 - Refer to [Appendix 4](#) for reproductive criteria for male ([Section 10.4.1](#)) and female ([Section 10.4.2](#)) participants.
2. Male and female participants who are overtly healthy as determined by medical evaluation including medical history, physical examination, including blood pressure, pulse rate, standard 12-lead ECG, and laboratory tests.

Other Inclusion Criteria:

3. BMI of 17.5 to 32 kg/m²; and a total body weight >50 kg (110 lb).

PFIZER CONFIDENTIAL

CT02-GSOP Clinical Pharmacology Protocol Template (01 April 2022)

Page 39

4. Capable of giving signed informed consent as described in [Appendix 1: Regulatory, Ethical, and Study Oversight Considerations](#) which includes compliance with requirements and restrictions listed in the ICD and in this protocol.

5.2. Exclusion Criteria

Participants are excluded from the study if any of the following criteria apply:

Medical Conditions:

1. Evidence or history of clinically significant hematological, renal, endocrine, pulmonary, gastrointestinal, cardiovascular, hepatic, psychiatric, neurological, or allergic disease (including drug allergies, but excluding untreated, asymptomatic, seasonal allergies at the time of dosing).
 - Any condition possibly affecting drug absorption (eg, gastrectomy, cholecystectomy).
 - History of HIV infection, hepatitis B, or hepatitis C; positive testing for HIV, HBsAg, HBcAb, or HCVAb. Hepatitis B vaccination is allowed.
 - Positive test result for SARS-CoV-2 infection on Day -1.
2. Participants, who according to the product label for moxifloxacin, would be at increased risk if dosed with moxifloxacin, including but not limited to participants with history of myasthenia gravis, tendinitis/tendon rupture, history of hypersensitivity, allergy, severe adverse drug reaction or intolerance to quinolone antibiotics, including moxifloxacin.
3. Self-reported history or risk factors for QT prolongation or torsades de pointes (eg, organic heart disease, congestive heart failure, hypokalemia, hypomagnesaemia, congenital long QT syndrome, myocardial ischemia or infarction), congenital deafness, family history of cardiac arrest or sudden death, and family history of long QT syndrome.
4. Other medical or psychiatric condition including recent (within the past year) or active suicidal ideation/behavior or laboratory abnormality or other conditions or situations related to COVID-19 pandemic that may increase the risk of study participation or, in the investigator's judgment, make the participant inappropriate for the study.

Prior/Concomitant Therapy:

5. Use of prescription or nonprescription drugs and dietary and herbal supplements within 7 days or 5 half-lives (whichever is longer) prior to the first dose of study intervention with the exception of antibiotics and moderate/strong CYP3A inducers or time-dependent inhibitors which are prohibited within 14 days plus 5 half-lives

prior to the first dose of study intervention. (Refer to Section 6.9 Prior and Concomitant Therapy for additional details).

6. Current use of any prohibited concomitant medication(s) or participant unwilling/unable to use a permitted concomitant medication(s).

Prior/Concurrent Clinical Study Experience:

7. Previous administration with an investigational product (drug or vaccine) within 30 days (or as determined by the local requirement) or 5 half-lives preceding the first dose of study intervention used in this study (whichever is longer).

Diagnostic Assessments:

8. A positive urine drug test.
9. For females, pregnancy, as indicated by a positive serum pregnancy test at screening and/or positive urine pregnancy test in WOCBP at Day -1.
10. Screening supine BP ≥ 140 mm Hg (systolic) or ≥ 90 mm Hg (diastolic), following at least 5 minutes of supine rest. If BP is ≥ 140 mm Hg (systolic) or ≥ 90 mm Hg (diastolic), the BP should be repeated 2 more times and the average of the 3 BP values should be used to determine the participant's eligibility.
11. Standard 12-lead ECG that demonstrates clinically relevant abnormalities that may affect participant safety or interpretation of study results (eg, QTcF >450 ms, complete LBBB, signs of an acute or indeterminate- age myocardial infarction, ST-T interval changes suggestive of myocardial ischemia, second- or third- degree AV block, or serious bradyarrhythmias or tachyarrhythmias). If the uncorrected QT interval is >450 ms, this interval should be rate-corrected using the Fridericia method only and the resulting QTcF should be used for decision making and reporting. If QTcF exceeds 450 ms, or QRS exceeds 120 ms, the ECG should be repeated twice and the average of the 3 QTcF or QRS values used to determine the participant's eligibility. Participants with an average QTc interval >450 milliseconds (ms) will not be allowed to participate in the study. Computer-interpreted ECGs should be overread by a physician experienced in reading ECGs before excluding a participant.
12. Participants with ANY of the following abnormalities in clinical laboratory tests at screening, as assessed by the study-specific laboratory and confirmed by a single repeat test, if deemed necessary:
 - GFR <60 mL/min/1.73m² based on CKD-EPI equation;
 - AST or ALT level $\geq 1.5 \times$ ULN;
 - Gamma-GT $> 1.2 \times$ ULN;

- Alkaline phosphatase $> 1.2 \times$ ULN;
- Total bilirubin level $\geq 1.5 \times$ ULN; participants with a history of Gilbert's syndrome may have direct bilirubin measured and would be eligible for this study provided the direct bilirubin level is \leq ULN.

Other Exclusion Criteria:

13. History of alcohol abuse or binge drinking and/or any other illicit drug use or dependence within 6 months of Screening. Binge drinking is defined as a pattern of 5 (male) and 4 (female) or more alcoholic drinks in about 2 hours. As a general rule, alcohol intake should not exceed 14 units per week (1 unit = 8 ounces (240 mL) beer, 1 ounce (30 mL) of 40% spirit, or 3 ounces (90 mL) of wine).
14. Use of tobacco or nicotine-containing products in excess of the equivalent of 5 cigarettes/day or 2 chews of tobacco/day.
15. Blood donation (excluding plasma donations) of approximately 1 pint (500 mL) or more within 60 days prior to dosing.
16. Unwilling or unable to comply with the criteria in the Lifestyle Considerations section of this protocol.
17. Investigator site staff directly involved in the conduct of the study and their family members, site staff otherwise supervised by the investigator, and sponsor and sponsor delegate employees directly involved in the conduct of the study and their family members.

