1.2. Schema

1.3. Schedule of Activities

The SoA table provides an overview of the protocol visits and procedures. Refer to the **STUDY ASSESSMENTS AND PROCEDURES** section of the protocol for detailed information on each procedure and assessment required for compliance with the protocol.

The investigator may schedule visits (unplanned visits) in addition to those listed in the SoA table, in order to conduct evaluations or assessments required to protect the well-being of the participant.

Table 1. Study Schedule of Assessment

Visit Identifier Abbreviations used in this table may be found in Appendix 10 .	Screen	Period 1 to Period 3														F/U Call	ET	Notes				
Days Relative to Day 1	Day -28 to Day -2	Day -1	Day 1	Day 2				Day 3							Day 4	31-38 Days						
Hours After Dose				0	1.5	4	5	6	12	0	1.5	3	4	5	6	8	12	24				
Informed consent	X																					
CRU confinement		X	→	→	→	→	→	→	→	→	→	→	→	→	→	→	→	X				
Inclusion/exclusion criteria	X	X																				
Medical/medication history	X	X																X				
Prior/concomitant treatments	X	X	→	→	→	→	→	→	→	→	→	→	→	→	→	→	→	X	X			
Physical exam	X	X																	X	X		

PFIZER CONFIDENTIAL

CT02-GSOP Clinical Pharmacology Protocol Template (01 April 2022)

Table 1. Study Schedule of Assessment

Visit Identifier Abbreviations used in this table may be found in Appendix 10.	Screen	Period 1 to Period 3														F/U Call	ET	Notes		
		Day -28 to Day -2	Day -1	Day 1	Day 2				Day 3							Day 4	31-38 Days			
Hours After Dose			0	1.5	4	5	6	12	0	1.5	3	4	5	6	8	12	24			
Safety laboratory	X	X		X													X	X		
 Participants should fast for at least 4 hours before safety labs are drawn. Includes urinalysis.
Demography	X																			
Pregnancy test (WOCBP only)	X	X																X		
 Day -1 pregnancy testing in Period 2 and 3 only if participant is discharged from CRU between periods. ET pregnancy testing only if participant withdraws while not admitted to the CRU.
Contraception check	X	X																X	X	X
FSH (post-menopausal women only)	X																			
Urine drug testing	X	X																		
 Day -1 urine drug testing in Period 2 and 3 only if participant is discharged from CRU between periods.

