Thymus effects	Lymphoid atrophy and decreased thymus weight and reduced size of thymus in both rats (≥ 120 mg/kg/day) and dogs ≥ 15 mg/kg/day) in studies of up to 28 days. Evidence of recovery following a 14-day treatment-free period. These findings are secondary to stress and not directly sisunatovir related	Standard monitoring including laboratory (i.e., complete blood count with differential) and AE monitoring. Brief 3-day course regimen should further limit this potential risk.
Study Intervention(s) moxifloxacin		
Gastrointestinal disturbances (eg, nausea, diarrhoea, vomiting)	Adverse reactions reported following moxifloxacin administration	A single dose of 400 mg will be administered in the study. Participants will be monitored for AEs in an inpatient clinical research unit.
Hypersensitivity reactions, including anaphylactic reactions	Adverse reactions reported following moxifloxacin administration	A single dose of 400 mg will be administered in the study. Participants will be monitored by vitals and for AEs in an inpatient clinical research unit. Participants with history of hypersensitivity or intolerance to quinolone antibiotics, including moxifloxacin, will be excluded.
Peripheral neuropathy, exacerbation of myasthenia gravis, and central nervous system effects including agitation, insomnia, dizziness and anxiety.	Adverse reactions reported following moxifloxacin administration	A single dose of 400 mg will be administered in the study. Participants will be monitored for AEs in an inpatient clinical research unit. Participants with history of myasthenia gravis are excluded.
Tendinitis and tendon rupture	Adverse reaction reported following moxifloxacin administration	A single dose of 400 mg will be administered in the study. Participants will be monitored

Potential Risk of Clinical Significance	Summary of Data/Rationale for Risk	Mitigation Strategy
		for AEs in an inpatient clinical research unit.
Prolongation of the QT interval and isolated cases of torsade de pointe	Adverse reaction reported following moxifloxacin administration	A single dose of 400 mg will be administered in the study. Participants will be monitored for cardiac changes (telemetry and ECG) and AEs in an inpatient clinical research unit. Participants with known history or risk factors for prolonged QT will be excluded.

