10.2. Appendix 2: Clinical Laboratory Tests

The following safety laboratory tests will be performed at times defined in the SoA section of this protocol. Additional laboratory results may be reported on these samples as a result of the method of analysis or the type of analyzer used by the clinical laboratory, or as derived from calculated values. These additional tests would not require additional collection of blood. Unscheduled clinical laboratory measurements may be obtained at any time during the study to assess any perceived safety issues.

Table 4. Protocol-Required Safety Laboratory Assessments

Hematology	Chemistry	Urinalysis	Other
Hemoglobin	Urea and creatinine	Local dipstick:	
• Pregnancy test (β-hCG)^d• Urine drug screening^c• Covid-19 testing
Hematocrit	CystatinC and eGFR	pH	
RBC count	Glucose (fasting)	Glucose (qual)	
Platelet count	Calcium	Protein (qual)	
WBC count	Sodium	Blood (qual)	
Total neutrophils (Abs)	Potassium	Ketones	At screening:
Eosinophils (Abs)	Chloride	Nitrites	
• FSH^b• Hepatitis B surface antigen
Monocytes (Abs)	Total CO ₂ (bicarbonate)	Leukocyte esterase	
• Hepatitis B surface antibody^e• Hepatitis B core antibody• Hepatitis C antibody• HIV
Basophils (Abs)	AST, ALT		
Lymphocytes (Abs)	GGT	Laboratory:	
	Total bilirubin	Microscopy and culture ^a	
	Alkaline phosphatase		
	Uric acid		
	Albumin		
	Total protein		

- a. Only if UTI is suspected and urine dipstick is positive for nitrites or leukocyte esterase or both.
- b. For confirmation of postmenopausal status only.
- c. The minimum requirement for drug screening includes cocaine, THC, opiates/opioids, benzodiazepines, and amphetamines (others are site and study specific).
- d. Local urine testing will be standard for the protocol unless serum testing is required by local regulation or IRB/EC. Serum or urine β -hCG for female participants of childbearing potential.
- e. HBsAb will be tested if HBsAg and/or HBcAb is positive.

The investigator must review the laboratory report, document this review, and record any clinically relevant changes occurring during the study in the AE section of the CRF.

Laboratory results that could unblind the study and have been collected for the purpose of the study will not be reported to investigator sites or other blinded personnel until the study has been unblinded.

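### The QT-risk exclusion names hypomagnesaemia, but no required pre-dose test measures magnesium

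*Protocol*

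**What the plan says.** Protocol 5.2, criterion 3 excludes "Self-reported history or risk factors for QT prolongation or torsades de pointes (eg, organic heart disease, congestive heart failure, hypokalemia, hypomagnesaemia", followed by further cardiac and family-history items. The synopsis repeats it.

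The laboratory tests the site must run are in Appendix 2 (10.2) under "Table 4. Protocol-Required Safety Laboratory Assessments". The chemistry column covers kidney function, fasting glucose, calcium, sodium, potassium, chloride, bicarbonate, liver tests, uric acid, albumin and total protein. Magnesium is not in it. The Schedule of Activities (1.3) places the safety laboratory at Screening and Day -1, among other times.

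Criterion 12 excludes "Participants with ANY of the following abnormalities in clinical laboratory tests at screening". Its list is GFR, AST or ALT, gamma-GT, alkaline phosphatase and total bilirubin.

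The risk table (2.3.1) gives several measures against moxifloxacin's QT effect: a single 400 mg dose, telemetry and ECG, adverse event monitoring in an inpatient unit, and an eligibility rule, "Participants with known history or risk factors for prolonged QT will be excluded".

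**The concern.** The protocol itself treats hypomagnesaemia as a reason not to enrol someone in this study. A healthy volunteer is unlikely to know a current magnesium value, and nothing the site is required to do supplies one. A listed exclusion therefore depends on what the participant happens to know.

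What is at stake is individual safety screening, and secondarily the reading of individual QTcF outliers. By design each participant who completes the three periods receives moxifloxacin, chosen because it prolongs QT, and also sisunatovir, which section 2.2.1 describes as a hERG inhibitor in vitro.

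**Working it through.** The plan states no figure on this point, so the check sets the provisions side by side.

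**1. Is magnesium measured?** Reading the chemistry column of Table 4 item by item: urea and creatinine, cystatin C and eGFR, glucose, calcium, sodium, potassium, chloride, total CO2, AST and ALT, GGT, total bilirubin, alkaline phosphatase, uric acid, albumin, total protein. There is no magnesium and no sign of redaction in the column. No other section requires the test.

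**2. Does another criterion reach it?**

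| Provision | Low potassium | Low magnesium |
|---|---|---|
| Required panel at Screening and Day -1 (Table 4, 1.3) | Measured | Not measured |
| Inclusion 2 (healthy on laboratory tests, among others) | Can act | No required value to act on |
| Criterion 4, "laboratory abnormality or other conditions or situations related to COVID-19 pandemic that may increase the risk of study participation" | Can act | No required value to act on |
| Criterion 12 (itemised laboratory list) | Not listed | Not listed |
| Criterion 2, "Participants, who according to the product label for moxifloxacin, would be at increased risk if dosed with moxifloxacin" | Requires no test | Requires no test |
| Criterion 3 (QT risk factors) | Named | Named |

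Of the two electrolyte disturbances named in criterion 3, one has a required pre-dose measurement and one does not.

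**3. Does the wording of criterion 3 change this?** If self-reported governs both history and risk factors, hypomagnesaemia excludes only when the participant discloses it. If it governs history alone, hypomagnesaemia excludes however it is found, but the plan prescribes no way of finding it. The gap stands on both readings.

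**4. How many people?** The documents give no prevalence. Assume that 1% to 5% of otherwise eligible volunteers have low magnesium, that none of them know it, and that participants are independent.

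- Expected number among 42: 42 × 0.01 = 0.42; 42 × 0.05 = 2.1.
- Chance of at least one: 1 − 0.99^42 ≈ 0.34; 1 − 0.95^42 ≈ 0.88.

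These figures illustrate scale and are not estimates from the trial. They count participants with the factor, not those harmed by it.

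**5. Does it reach the statistics?** The power calculation in 9.5 uses a 10 msec expected moxifloxacin effect, a 5 msec threshold, an SD of 5.61 msec and 42 participants. None depends on this point. Each participant serves as their own control with a new baseline in each period, so a stable low magnesium would be present under all three treatments.

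**The case against.** The strongest case on the other side is that the remaining risk is small and the plan has several layers of protection. Criterion 11 excludes an average QTc above 450 ms. Criterion 12 excludes reduced GFR, and other criteria exclude gastrointestinal, renal and endocrine disease, alcohol abuse, and recent drug or supplement use. Section 8.3.3 sets QTcF triggers for repeat and continuous ECG monitoring, and telemetry is planned for the moxifloxacin risk. What is left is unrecognised low magnesium in a screened volunteer with an acceptable QTcF. This stands, and it keeps the point modest. But these safeguards detect prolongation or exclude other conditions; none measures the factor that criterion 3 names.

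A reader might infer four stronger things that the documents do not support:

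- *That the site cannot detect low magnesium.* Section 8.3.4 and Appendix 2 allow unscheduled tests for perceived safety issues, and Appendix 2 notes that the analyzer may report additional results. A known case can also be disclosed. What is missing is a required test.
- *That potassium is equally unchecked.* It is measured before dosing, and inclusion 2 or criterion 4 can act on a low value. Its absence from criterion 12 leaves the limit unstated but does not leave potassium unmeasured.
- *That the exclusion is the sole mitigation for moxifloxacin.* Section 2.3.1 lists it as one of several, and speaks of known risk factors, which is compatible with self-report. The risk table and criterion 3 do not contradict each other.
- *That a QTcF outlier could never be checked against magnesium.* Appendix 2 lets leftover safety samples be kept and used after the study for unexpected safety findings. That route is optional and retrospective, so it protects nobody before dosing, but it exists.

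A link from sisunatovir's gastrointestinal events to magnesium loss would also be an inference; no section makes it.

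**Conclusion.** The point holds for magnesium only. A named exclusion factor has no required pre-dose test, because Table 4 omits the analyte and criterion 12 lists no electrolyte. This is a gap between an eligibility rule and the procedures meant to support it. It bears on individual safety screening and leaves the mean treatment contrasts, alpha and power untouched.

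Its size cannot be fixed from the documents; the expected 0.4 to 2.1 of 42 participants rests wholly on the assumed 1% to 5% prevalence. The conclusion itself needs no prevalence. It rests on the chemistry column of Table 4 being complete as published. The change is worth making because it is cheap and makes a stated exclusion checkable.

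**What to change.** Reconcile criterion 3, criterion 12 and Table 4:

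- Add serum magnesium to the Table 4 chemistry panel at the safety-laboratory times already in the Schedule of Activities.
- State in criterion 3, or by cross-reference from criterion 12, whether the named electrolyte risk factors are judged on measured screening values, on participant report, or on both. Make the same change in the synopsis.
- Leave any limits to the sponsor's clinicians.

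The cost is one extra analyte on blood already drawn, a short wording change, and possibly an additional screen failure. No change to the SAP, the sample size or the analysis models follows from it.
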